#### **Aim 3**

Memory sparing will be compared between *APOE4+* and *APOE4-* participants using Fisher's exact tests to compare the proportion of *APOE4+* and *APOE4-* participants between the LEADS participants in each atypical subtype of EOAD. Differences between MRI/PET measures of *APOE+* and non-carriers will be assessed at baseline and longitudinally using multiple linear models and linear mixed models after controlling for potential confounders (e.g. education and sex). The results will be presented using graphical representations. The rates of *APOE4+* and *APOE4-* participants will be compared between EOAD and EOnonAD participants will be compared using Fisher's exact tests.

#### **Aim 4**

Research-based genetic screening will be performed in a research laboratory. Established pipelines will be used for processing and annotating sequencing variants. Known pathogenic mutations in the six screened genes will be confirmed by a CLIA-certified laboratory. Sequence data will be generated in a research laboratory and combined with publicly available sequence data from the Alzheimer Disease Sequencing Project (ADSP; phs000572.v1.p1). Gene-based case-control tests will be used to identify genes and pathways with a greater burden of rare variants in cognitively impaired as compared with CN individuals.

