## PROTOCOL SYNOPSIS

PROTOCOL TITLE	Longitudinal Early-onset Alzheimer's Disease Study (LEADS)
PROJECT DIRECTOR/PRINCIPAL INVESTIGATOR	[name]., M.Sc.
STUDY DESIGN	Non-randomized, natural history, non-treatment study
STUDY COMPOUNDS	Florbetaben Flortaucipir Fluorodeoxyglucose (FDG) Pittsburgh Compound B (PiB) (for International sites only) NAV-4694 (Flutafuranol) (for International sites only) Flutemetamol (for International sites only)
RECRUITMENT GOALS AND DURATION OF STUDY	Up to 850 cognitively impaired participants (in the US) = 3+ Years in duration 
 
• Approximately 650 EOAD participants
 
• Approximately 200 EOnonAD participants
 
 100 CN participants = 2+ Years in duration 40 cognitively impaired participants (across international sites) = 3 + Years in duration 10 CN participants (across international sites) = 2+ Years in duration Screening period = < 60 days (including baseline assessments)
SUMMARY OF KEY ELIGIBILITY CRITERIA	Cognitively Impaired Cohorts: 
 
• Diagnosis of NIA-AA criteria of MCI or dementia due to probable AD
 
• CDR score ≤ 1.0
 
 Cognitively Normal Cohort:

	
 
• Meets criteria for cognitively normal, based on an absence of significant impairment in cognitive functions and activities of daily living
 
• Mini-Mental State Exam score between 26-30
 
• CDR score = 0
 
 
Both Cohorts:
 
 
• 40-64 (inclusive) years of age at the time of consent
 
• Willing and able to undergo study procedures as outlined in the Schedule of Events
 
• Must have study partner (informant) who spends a minimum average of 10 hours per week with the participant.
 

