## 1.0 BACKGROUND AND SIGNIFICANCE

While the risk of AD increases with advancing age, approximately 5% of AD patients develop symptoms before age 65 (~280,000 Americans). Patients with early-onset Alzheimer's disease (EOAD), occurring before the age of 65, are an understudied segment of the patient population with Alzheimer's Disease (AD). Many treatment studies exclude these younger individuals.

Of the two major North American consortia, ADNI includes only a few EOAD cases all with a “typical” amnestic presentation and the Dominantly Inherited Alzheimer Network (DIAN) focuses solely on autosomal dominant AD (ADAD). Clinical and neuroimaging measures that emphasize episodic memory and medial temporal neurodegeneration in

LOAD are insensitive to the baseline deficits and the disease progression in EOAD, which predominantly involve non-memory cognitive domains and posterior cortical neurodegeneration. The overarching aim of this Longitudinal Early-Onset AD Study (LEADS) is to fill this gap in AD research by conducting a clinical and biomarker study in the EOAD population.

LEADS includes key AD research sites across the U.S. and will leverage existing infrastructure and processes applied in ADNI. The over-arching goals are to advance our knowledge about disease mechanisms and develop sensitive composite clinical and biomarker tools that capture disease progression in this unique cohort for implementation in clinical trials. Our secondary goals include: (1) collection of DNA from EOAD participants for exploratory studies applying next generation sequencing; (2) collection and banking of clinical, biofluid and imaging measures for future research and sharing with the larger research community; and (3) establishing a network of EOAD sites that will enable future planning and implementation of clinical trials in EOAD. While the research is focused on EOAD, LEADS will also follow individuals who meet clinical criteria for MCI or dementia due to probable AD but have a negative amyloid PET scan (EOnonAD) with the goal to generate important scientific knowledge about this patient population.

Data collected in this study will address several significant gaps in AD research. In addition to affording this highly motivated population the chance to contribute to AD research, EOAD patients offer the opportunity to study a more “pure” form of AD with fewer age-related brain co-pathologies[1, 2].

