**Rationale for Aim 3:** *APOE4*+, the most significant genetic risk factor for sporadic AD [18], exerts its maximal effects between ages 65-75[19, 20]. The prevalence of *APOE4*+ is substantially lower in EOAD than in LOAD[21]. Furthermore, *APOE4* seems to moderate the phenotype of AD by predisposing to MTL vulnerability[15, 22-29]. Greater memory impairment and MTL atrophy in *APOE4*+ AD, and greater non- amnestic presentations and cortical atrophy in *APOE4*- subjects has been reported by some [23, 26-28, 30-33] but not others[34, 35]. Yet since most of these clinical studies lack pathologic or biomarker confirmation of AD pathology, the perceived differences might be driven by increased rates of non-AD pathology in *APOE4*- individuals, necessitating a more definitive study. Furthermore, *APOE* genotype is emerging as a major pharmacogenomic consideration for AD trials. It is therefore critical to stratify EOAD and EOnonAD participants and determine

how rates and patterns of atrophy, A $\beta$  and tau accumulation may differ on the basis of *APOE* genotype.

### 3.4 Exploratory Aim 4

To characterize genetic contributions to EOAD and obtain annually an array of uniformly collected biospecimens for future biomarker development.

**H4a:** A subset of EOAD will have mutations in genes known to contribute to AD.

**H4b:** A subset of EOnonAD will have mutations in genes known to contribute to FTLD.

**H4c:** Next generation sequencing will identify novel genes in EOAD involved in A $\beta$ , tau, inflammation and lipid processing pathways.

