**Rationale for Aim 4:** Pedigree analyses suggest that apparently “sporadic” EOAD is a highly heritable condition, recognized pathogenic mutations in *APP*, *PSEN1* and *PSEN2* are rarely identified in these subjects, and much of the measured heritability of EOAD remains unexplained even after accounting for *APOE4* [36, 37]. Few studies have amassed a large enough sample of sporadic EOAD to be sufficiently powered to identify new genes contributing to disease risk. Next generation sequencing has rarely been applied to this population, yet is well suited to identify rare genes with large effects, recessive or de novo mutations and other more complex heritability patterns. This study’s cohort (400 deeply phenotyped sporadic EOAD without a known genetic etiology) will be the focus of this exploratory aim to initiate new gene discovery, which may lead to insights into novel disease mechanisms and pathways. We propose to apply innovative genetic approaches (i.e., whole genome sequencing and epigenetic analyses) to study vulnerability in EOAD. In addition, we will investigate the influence of *APOE* genotype on cognitive, imaging and biofluid biomarkers, which is critical to help plan pharmacogenomic approaches in AD clinical trials.

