## 4.0 STUDY DESIGN AND INVESTIGATIONAL PLAN

The LEADS design builds on the success of two major natural history/biomarker initiatives in AD: ADNI and DIAN. Like those initiatives, the LEADS approach links longitudinal clinical and cognitive assessments with multiple imaging and biofluid markers that capture different elements of the AD pathophysiological cascade. Its alignment to ADNI will allow us to use ADNI LOAD participants as a disease comparison group.

LEADS is a non-randomized, natural history, non-treatment study. Approximately 850 cognitively impaired (EOAD and EOnonAD) participants and 100 CN participants will be enrolled at approximately 20 sites in the United States. Approximately 40 CI participants and 10 CN participants will be enrolled in sites outside of the U.S. as a part of iLEADS, the international expansion of LEADS. Clinical/cognitive, imaging, biomarker, and genetic characteristics will be assessed across the three cohorts: EOAD, EOnonAD, and CN.

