### **5.0 STUDY POPULATION**

#### **5.1 Inclusion Criteria**

##### Cognitively impaired (EOAD and EOnonAD) Cohorts Only:

1. Meets NIA-AA criteria for MCI due to AD or probable AD dementia
2. Have a global CDR score  $\leq 1.0$
3. Have capacity to provide informed consent (IC) or has a legal authorized representative or guardian who provides IC
4. Age between 40-64 years (inclusive) at the time of consent
5. Must have a study partner (informant) who spends a minimum average of 10 hours per week with the participant (e.g., family member, significant other, friend, caregiver) who is generally aware of the participants' daily activities and can provide information about the participant's cognitive and functional performance. If the participant does not have a study partner who spends at least 10 face-to-face hours per week, other arrangements for identifying a viable study partner will be granted on a case-by-case basis by the Site PI
6. Willing and able to complete longitudinal study procedures aside from LP which is an optional procedure
7. Not pregnant or lactating. Women must be two years post-menopausal, be surgically sterile, or have a negative pregnancy test prior to each PET scan
8. Fluent in English or Spanish if enrolled in the U.S.
9. Fluent in English, Spanish, Dutch or Swedish for sites outside the U.S., according to site's spoken language(s).

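### The Aim 4 gene-burden test takes all cognitively impaired participants as cases, although the objective and H4c concern EOAD only

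*Protocol*

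**What the plan says.** **The test.** Protocol section 21.1.2, Aim 4, combines LEADS sequence data with public ADSP data. In a case-control comparison by gene, "tests will be used to identify genes and pathways with a greater burden of rare variants in cognitively impaired as compared with CN individuals".

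**The label.** Section 4.0 fixes what cognitively impaired means: "Approximately 850 cognitively impaired (EOAD and EOnonAD) participants and 100 CN participants will be enrolled". Section 5.1 repeats it in the heading "Cognitively impaired (EOAD and EOnonAD) Cohorts Only". Section 1.0 describes EOnonAD as people who meet the clinical criteria but have a negative amyloid PET scan. The synopsis plans "Approximately 200 EOnonAD participants" and about 650 EOAD in the US.

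**The question.** The Aim 4 objective in section 3.4 begins "To characterize genetic contributions to EOAD and obtain annually an array of uniformly collected biospecimens". H4c reads "Next generation sequencing will identify novel genes in EOAD involved in" several named pathways. The rationale names "400 deeply phenotyped sporadic EOAD without a known genetic etiology" as the focus for gene discovery.

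**The power statement.** Section 21.1.4, Aim 4, claims 80% power for odds ratios of 1.5 to 3.0 over 171 genes at alpha 2.9 × 10⁻⁴. It gives no number of cases or controls.

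**The concern.** The cases in the test are a wider population than the one in the hypothesis. If a gene shows an excess of rare variants in the mixed group, the excess may come from EOAD, from EOnonAD or from both. H4c asks only about EOAD. Aim 5 treats EOnonAD as a group whose causes are still to be found, so those participants cannot be assumed to stand in for EOAD.

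The label does not look like a slip that readers would correct for themselves. Elsewhere section 21.1.2 names the cohorts separately: the opening paragraph gives EOnonAD its own exploratory analysis, Aim 3 compares EOAD with EOnonAD, and Aim 5 compares CN with EOnonAD. An analysis plan that followed the Aim 4 sentence would carry the mismatch forward.

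**Working it through.** **1. Population of the hypothesis and of the test**
- Objective, H4c and rationale (section 3.4): EOAD. The rationale narrows this to sporadic EOAD with no known genetic cause.
- Burden test (section 21.1.2, Aim 4): cognitively impaired, meaning EOAD plus EOnonAD (sections 4.0 and 5.1).
- H4b does concern EOnonAD, but only mutations in genes already known for FTLD. The six-gene screen in section 7.2, which includes MAPT, GRN and C9ORF72, addresses that without the burden test.
- Section 21 describes no EOAD-only burden test.

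**2. EOnonAD share of the cases**
- LEADS US only: 200/850 = 23.5%.
- With the rationale's 400 EOAD in place of 650: 200/600 = 33.3%.
- With an assumed 1,000 or 5,000 ADSP cases: 200/1,850 = 10.8%, or 200/5,850 = 3.4%.

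**3. The plan's own figures**
- 0.05/171 = 2.92 × 10⁻⁴, which matches the stated alpha.
- The 80% power cannot be reproduced, because no case number, control number or carrier rate is given.

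**4. Dilution of the odds ratio**

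Let p0 be the carrier rate in controls, p1 the rate in EOAD, and s the share of the EOAD excess that EOnonAD carry. The mixed rate is pm = [650·p1 + 200·(p0 + s·(p1 − p0))]/850.

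Example with assumed p0 = 5%, true OR 2.0 and s = 0:
- odds in EOAD = 2 × 0.05/0.95 = 0.1053, so p1 = 0.0952
- pm = (650 × 0.0952 + 200 × 0.05)/850 = 0.0846
- apparent OR = (0.0846/0.9154)/(0.05/0.95) = 1.76

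The same steps turn 1.5 into 1.38 and 3.0 into about 2.5. These values barely change for p0 from 1% to 5%.

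**5. Power**

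Power = Φ[(|p1 − p0| − z·SE0)/SE1], two-sided with z = 3.624. SE1 is the unpooled standard error. SE0 is the standard error under the null, pooled or unpooled.

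Same example with 5,000 assumed controls and pooled SE0:
- 650 EOAD: (0.04524 − 3.624 × 0.00952)/0.01192 = 0.90, power 81.6%
- 850 mixed: 65.3% (s = 0), 81.1% (s = 0.5), 91.1% (s = 1)

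For a range, I took p0 from 1% to 5% and 650 to 100,000 controls, solved for the OR giving 80% power with 650 EOAD, kept ORs up to 3.0, and recomputed power with the 200 EOnonAD added:

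| ADSP cases (assumed) | EOnonAD carry | Pooled SE0 | Unpooled SE0 |
|---|---|---|---|
| none | none of the excess | 54–69% | 60–72% |
| none | half | 72–82% | 78–85% |
| none | all | 86–91% | 90–93% |
| 1,000 (5,000 controls) | none | 72–73% | 73–76% |
| 5,000 (5,000 controls) | none | 77% | 77–78% |

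In the last two rows the ADSP cases are assumed to carry the full excess, and the 80% reference is EOAD plus ADSP cases.

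**6. Does the grid fit the power statement?** Without ADSP cases, the smallest OR that reaches 80% power with 650 EOAD is 1.89 (pooled SE0) or 2.19 (unpooled). The stated lower end of 1.5 is never reached. With 5,000 ADSP cases the 80%-power ORs run from about 1.44 to 2.10, which covers it.

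**The case against.** **Section 21 is a brief summary, and section 3.4 already names the discovery cohort.** The first part is true. But the sentence does state a case group, and it differs from the one in section 3.4. This is a conflict between two stated populations, not detail left for later.

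**Aim 4 is not purely about EOAD, because of H4b.** That may explain the umbrella term. It does not justify it for the burden test, since H4b concerns known genes.

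**Some EOnonAD may have AD.** The Aim 5 rationale and the Month 36 tau PET footnote in Appendix 1 allow for this. It supports keeping a pooled analysis, but not as the only one stated.

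**Three stronger readings are tempting and are not supported:**
- *Pooling costs power.* Against a reference of 80%, the result runs from 54% to 93% on inputs that the protocol does not give. The largest losses come from scenarios without ADSP cases, which do not reach the OR of 1.5 in the protocol's own power statement.
- *Some 23.5% of the test's cases are EOnonAD.* That is the share among LEADS US impaired participants only. The test adds ADSP data, and the protocol does not say how many cases those contribute.
- *This is the protocol's only gene-discovery work.* It is the only such test in section 21. Section 4.1.5 also assigns candidate pathway and genome-wide analyses to the Genetics and Biorepository Core.

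It also stands that Aim 4 is labelled exploratory, and that amyloid status is recorded, so an EOAD-only test can be run later from the same data.

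**Conclusion.** The mismatch is real and rests on the protocol's own definitions. The burden test as written compares a mixed EOAD and EOnonAD group with CN, while the objective, H4c and the rationale concern EOAD. A positive result could not be attributed to EOAD without a further analysis that section 21 does not state. This conclusion needs no assumption about carrier rates or ADSP numbers.

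The effect on power is undetermined. It is a loss if EOnonAD carry little of the excess and ADSP adds few cases, a loss of about 2 to 3 points if ADSP adds an assumed 5,000 cases, and a gain if EOnonAD share most of the excess. Because the aim is exploratory and the data are kept, this is a worthwhile correction of modest priority.

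**What to change.** - **Section 21.1.2, Aim 4:** name EOAD participants without a known pathogenic variant in the six screened genes (APP, PSEN1, PSEN2, MAPT, GRN, C9ORF72) as the cases for the H4c burden test. Keep the comparison of all cognitively impaired participants with CN as a secondary analysis.
- **Section 21.1.4, Aim 4:** tie the 80% power statement to that case set and give its case and control numbers, including what ADSP contributes to each. Reconcile the 400 EOAD in the section 3.4 rationale with the 650 in section 21.1.4.
- **H4b** needs no change.

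The cost is one or two sentences in each place. Amyloid status and the six-gene screen are already collected. The downside is a smaller nominal case group and some power given up if EOnonAD share most of the genetic effect: where 650 EOAD have 80%, the pooled 850 would then have 86–93% (no ADSP cases). Keeping the pooled comparison as secondary preserves that information.

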#### **Aim 5**

t-tests, non-parametric tests, and Analysis of Variance (ANOVA) models will be used to compare clinical domain scores between CN and EOnonAD participants. Multiple linear regression models will be used to investigate whether FDG PET is more sensitive than MRI when identifying changes in neurodegeneration in EOnonAD cohort. Unsupervised clustering methods will be utilized to find groups of participants in the EOnonAD cohort with similar imaging and clinical characteristics and identify potential etiologies in EOnonAD.

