##### Cognitively Normal (CN) Cohort Only:

1. Meets criteria for cognitively normal, based on an absence of significant impairment in cognitive functions or activities of daily living
2. Have a global CDR score = 0
3. Have capacity to provide informed consent
4. Have a Mini-Mental State Exam score between 26-30 (inclusive). Exceptions may be made for participant with less than 8 years of education at the discretion of the Site PI
5. Age between 40-64 years (inclusive) at the time of consent
6. Must have a study partner (informant) who spends a minimum average of 10 hours per week with the participant (e.g., family member, significant other, friend, caregiver) who is generally aware of the participants' daily activities and can provide information about the participant's cognitive and functional performance. If the participant does not have a study partner who spends 10 face-to-face hours per week, other arrangements for identifying a viable study partner will be granted on a case-by-case basis by the Site PI
7. Willing and able to complete longitudinal study procedures aside from LP which is an optional procedure
8. Not pregnant or lactating. Women must be two years post-menopausal, be surgically sterile, or have a negative pregnancy test prior to each PET scan
9. Fluent in English or Spanish if enrolled in the U.S.
10. Fluent in English, Spanish, Dutch or Swedish for sites outside the U.S., according to site's spoken language(s).

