## **7.2 Clinical Assessments and Procedures**

### ***Demographics***

Participants and study informants will provide basic demographic information throughout the study.

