#### ***Aim 1***

Baseline composite cognitive scores will be developed using clustering techniques such as kNN clustering. The cognitive data will be collected in integer scales for each test. Differences of the composite scores within cognitive domains between

LEADS EOAD and ADNI LOAD participants will be assessed using multivariate linear regression controlling for the effects of candidate confounders such as education and sex. The results will be presented using graphical methods and tables of statistical summary estimates and test results. Longitudinal changes in cognitive scores will be assessed using linear mixed models and machine learning approaches.

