#### **Aim 2**

MRI and PET based biomarker volumes computed at the mm^3 scale, will be used to assess baseline and longitudinal associations of composite cognitive scores and imaging metrics and identify differences between LEADS EOAD and ADNI LOAD participants. Specifically, multiple linear regression analysis will be used to identify differences between imaging-based metrics in LEADS EOAD vs. ADNI LOAD at baseline and to assess correlations between composite cognitive and imaging measures, while longitudinal data will be analyzed using mixed effects models when data for more than 2 visits per participant is collected. Relevant confounders (e.g. sex, education) will be included as covariates. In addition, summary MRI and PET measures will be analyzed using machine learning techniques to identify a composite metric capturing change across LEADS EOAD participants.

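### Aim 5 names no covariates for the CN versus EOnonAD comparison of domain scores, although the groups are not randomised and the regression models of Aims 1 to 3 control for education and sex

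*Protocol*

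**What the plan says.** Aim 5 in section 21.1.2 fixes the method for the group comparison: "t-tests, non-parametric tests, and Analysis of Variance (ANOVA) models will be used to compare clinical domain scores between CN and EOnonAD participants". No covariate is attached. The same paragraph then mentions a regression, but for a different question within one cohort: "Multiple linear regression models will be used to investigate whether FDG PET is more sensitive than MRI when identifying changes in neurodegeneration in EOnonAD cohort".

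Section 4.0 describes the design: "LEADS is a non-randomized, natural history, non-treatment study".

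The regression models in the neighbouring aims do carry covariates:

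- Aim 1, cognitive domain composites in EOAD and LOAD: "controlling for the effects of candidate confounders such as education and sex".
- Aim 2, imaging measures: "Relevant confounders (e.g. sex, education) will be included as covariates".
- Aim 3, MRI and PET measures by APOE4 status: "after controlling for potential confounders (e.g. education and sex".

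All three lists are open-ended. None of them names age.

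The data are at hand. Section 7.2 says "Participants and study informants will provide basic demographic information throughout the study", and age is known at entry because it is an eligibility criterion for the CN cohort ("Age between 40-64 years (inclusive) at the time of consent") and, with the same limits, for the impaired cohorts.

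**The concern.** Cognitive test scores commonly vary with education, sex and age. The protocol itself allows for education: the MMSE criterion for CN participants may be relaxed for people with fewer than 8 years of schooling (section 5.1). Nothing in the eligibility criteria matches CN to EOnonAD participants on education or sex. The shared 40 to 64 age window limits an age imbalance but does not remove it.

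A t-test or a standard rank test cannot correct for such imbalance. What is at stake is mainly description. A difference between the groups is expected from the way they are selected, so the informative output is how large it is and how it varies across domains. If education or sex acts more strongly on some domains than on others, an imbalance changes that pattern as well as the overall size.

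**Working it through.** **Text comparison.** Aim 1 is the closest parallel: cognitive domain scores compared between two non-randomised groups by regression with covariates. Aim 5 also compares domain scores between two non-randomised groups, but names tests without covariates and gives no reason for the difference. The regression in Aim 5 does not fill the gap, because it concerns FDG PET against MRI within EOnonAD.

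**Is there a figure in the plan to reproduce?** No. Section 21.1.4 sets 90% power at a significance level of 0.05 in general and gives detail for Aims 1 to 4 only. What follows is an illustration.

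**Inputs.**

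- From the synopsis (US figures): about 200 EOnonAD and 100 CN.
- From section 21.1.4: significance level 0.05. Sidedness is not stated; two-sided is assumed.
- Assumed, not in the protocol: *d*, the between-group imbalance in a covariate, in SD; and *r*, the within-group standardised slope of the score on that covariate.

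**Standard error of an unadjusted difference.** SE = √(1/200 + 1/100) = 0.122 SD. The difference detectable with 90% power is 0.122 × (1.960 + 1.282) = 0.397 SD.

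**Bias.** Shift *b* = *r* × *d*. If a domain had no true adjusted difference, an unadjusted test would reject with probability P(|N(*b*/SE, 1)| > 1.96):

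| *r* | *d* | Shift *b* (SD) | Rejection probability |
|---|---|---|---|
| 0.1 | 0.2 | 0.02 | 5.3% |
| 0.1 | 0.5 | 0.05 | 6.9% |
| 0.3 | 0.2 | 0.06 | 7.8% |
| 0.5 | 0.2 | 0.10 | 12.9% |
| 0.3 | 0.5 | 0.15 | 23.2% |
| 0.4 | 0.5 | 0.20 | 37% |
| 0.5 | 0.5 | 0.25 | 53.2% |
| 0.6 | 0.5 | 0.30 | 69% |

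The result runs from negligible to large, depending wholly on the assumed *r* and *d*.

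**Precision.** If covariates explain a share R² of the within-group variance, the SE is multiplied by √(1 − R²): 0.949 for R² = 0.10 and 0.837 for R² = 0.30, a gain of 5% to 16%. That ignores the cost of imbalance. With *d* = 0.5 and a 200:100 split, the variance inflation is 1 + (2/9)(0.25) = 1.056. The multipliers become √(0.90 × 1.056) = 0.975 and √(0.70 × 1.056) = 0.860, so the net gain is about 2.5% to 14%.

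**The case against.** The strongest reply is that this is an exploratory comparison whose covariates would normally be listed in a statistical analysis plan, which is not shown. Section 21.1 says it describes the goals only briefly, section 21.1.2 calls the EOnonAD work exploratory, and no power statement covers Aim 5. ANOVA models can also carry further factors, and the text nowhere calls the comparison unadjusted. This stands as a limit on weight. It does not remove the point: the protocol names methods here, two of the three kinds in their usual form take no covariates, and the comparable analysis in Aim 1 is written differently.

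A reader might also infer more than the protocol supports:

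- *That the other aims adjust for age.* They name education and sex only.
- *That Aim 5 alone lacks adjustment.* The Fisher's exact tests on carrier rates in Aim 3 have no covariates either, and Aim 4 names none. The contrast is with the regression models of Aims 1 to 3.
- *That inference about aetiology would be distorted.* The protocol assigns that task to clustering within the EOnonAD cohort. H5a and H5b rest on imaging and plasma markers. None of H5a to H5c is a CN versus EOnonAD contrast in cognitive scores.
- *That false-positive rates would be high.* Those rates require a domain with no true difference. CN participants need CDR 0 and normally MMSE 26 to 30, while impaired participants must meet MCI or dementia criteria, so separation is largely built in. A spared domain is possible, but the protocol identifies none.

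**Conclusion.** The point holds as a minor one and as an improvement that costs nothing. Aim 5 specifies a non-randomised comparison of domain scores without naming covariates, while the regression models of Aims 1 to 3 control for education and sex. The likely harm is a biased size and pattern of domain differences, rather than a wrong conclusion about whether the groups differ.

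Its magnitude cannot be fixed from the protocol. The range of 0.02 to 0.3 SD, against an SE of 0.122 SD, rests on assumed imbalances of 0.2 to 0.5 SD, assumed slopes of 0.1 to 0.6, and full recruitment of about 200 EOnonAD and 100 CN participants in the US. The gain in precision is a secondary benefit, and a modest one once imbalance is counted. No stated hypothesis depends on this comparison.

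**What to change.** In Aim 5, make the main CN versus EOnonAD comparison a linear model (ANCOVA) for each domain score, with group, education and sex as in the regression models of Aims 1 to 3, plus age. Use a robust or rank-based version where scores are skewed. Keep the t-tests, non-parametric tests and ANOVA as unadjusted description alongside it.

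Age goes beyond what Aims 1 to 3 name, so it should be stated expressly. The cost is about one sentence of text: age is recorded for eligibility, demographics are already collected, and education and sex are already planned as covariates elsewhere. Sample size and visit schedule do not change.
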